9.19. Pharmacodynamics

Pharmacodynamic measurements will be performed according to the study's SOP and outlined in the SOA. These assessments will include changes in exosome biomarkers of pre-programmed cell death, synaptic integrity and function, and neuroinflammation will be assessed.

The pre-programmed cell death panel (PNCDD) will investigate key factors such as BAX, Bcl-2, which will provide insights into preprogrammed cell death processes (4,17) and any changes in the profile observed following treatment with phenserine or donepezil. The second panel focuses on synaptic markers, including synaptotagmin, offering a nuanced understanding of synaptic integrity and function. The third panel is centered on evaluating inflammatory biomarkers, including TNF- α , IL-1 β , IL-6, and IL10, and the fourth panel will evaluate AD-specific markers, including A β 1-42, and will elucidate key molecular signatures associated with AD pathology. This comprehensive evaluation of mechanistic biomarkers through exosome technologies aims to deliver a detailed understanding of the impact of phenserine versus donepezil on various facets of AD neuropathology.

The second panel focuses on synaptic markers, offering a nuanced understanding of synaptic integrity and function.

The third panel is centered on evaluating inflammatory biomarkers.

The fourth panel will evaluate AD-specific markers, elucidating key molecular signatures associated with AD pathology.

Additionally, pharmacodynamic effects related to AChE inhibition will be evaluated. AChE activity will be measured to assess the degree of enzyme inhibition achieved by phenserine compared to donepezil. The inhibition levels will be correlated with both clinical outcomes and other biomarker changes to provide a comprehensive view of the drug's pharmacodynamic profile.

9.20. Genetics

Genetics are not evaluated in this study.

9.21. Biomarkers

Blood and CSF biomarker samples will be collected at Screening and Week 8, while exosomal biomarkers will be assessed at Baseline, Week 2, Week 4, Week 6, and Week 8. This comprehensive evaluation of mechanistic biomarkers through exosome technologies aims to deliver a detailed understanding of the impact of phenserine versus donepezil on various facets of AD neuropathology, contributing to the trial's primary objective.

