1.3. Schedule of Activities (SoA)**Table 1. Schedule of Activities**

	Screening (within 28 days before baseline)	Treatment Period					Safety Follow-up ¹ /EOS (within 28 days after last visit)
		Baseline	W2	W4	W6	W8	
Days \pm Visit window	-28 to 0	0	(14\pm 3)	(28\pm 3)	(42\pm 3)	(56\pm 3)	(56\pm 28)
Informed consent	X						
Demographics	X						
Medical history ²	X						
Concomitant medications	X	X	X	X	X	X	X
Vital signs	X	X	X	X	X	X	X
Physical Exam	X	X	X	X	X	X	X
Neurological Exam	X						X
ECG	X	X	X	X	X	X	X
MMSE	X						
MoCA		X				X	
CDR	X						
MRI ³	X						
Suicidal screening using C-SSRS, modified ⁴	X			X		X	X
Inclusion/Exclusion criteria	X	X					
Randomization		X					
Dispense of IMP ⁵		X	X	X	X		
Adverse events		X	X	X	X	X	
AchE sample collection		X	X	X	X	X	

Dose review (for escalation or de-escalation)			X	X	X		
Exosome Biomarker Collection		X	X	X	X	X	
Blood and CSF-based biomarkers ⁶	X					X ⁷	
PK sample collection			X	X	X	X	
Safety laboratory test ⁸	X		X	X	X	X	X
Urinalysis	X		X	X	X	X	X
FSH test ⁹	X						
Pregnancy test ¹⁰	X		X		X		
FLAME Cognitive battery		X				X	

¹ A safety follow-up visit will be conducted within ~4-weeks after the last study-drug dose for all participants who complete the study or who terminate early.

² Includes prior medication use.

³ Only if no MRI scan available within last 2 years.

⁴ The C-SSRS will only be conducted at the follow-up/EOS visit, if the patient experienced suicidal thoughts after the study treatment period.

⁵ Before any dose escalation. According to tolerability and laboratory tests, the dosage will be reassessed, and participants may need to return to the center for a reduced dose.

⁶ CSF samples will only be collected from patients who specifically consent to CSF sample collection and analysis. If CSF biomarker data are available then there is no need for a new CSF collection at screening

⁷ CSF collection at W8 is voluntary and requires an additional informed consent.

⁸ Renal and liver function will be taken every visit. Full Safety laboratory battery will be taken at screening and safety follow-up.

⁹ Women considered post-menopausal will have an FSH test to confirm their status during the screening period and prior to dosing.

¹⁰ Pregnancy testing is required for all women of childbearing potential within one day prior to receiving the first dose of study drug.

2. Introduction

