5.1. Inclusion Criteria

1. A diagnosis of AD based on the most recent NIA-AA diagnostic criteria for AD (27).
2. A significant change on a validated AD amyloid or tau biomarker (as determined either by visual reading of amyloid PET scans [using any of the approved ligands], or CSF A β 1-42 or blood p-tau 217 levels [cut-off as determined by the individual laboratory]).
3. MCI (FDA stage 3) or mild dementia (FDA stage 4) based on a CDR Global rating of 0.5 (MCI) or 1.0 (mild dementia) (28)
4. An MRI scan within the past two years that has no findings inconsistent with AD.
5. Participants who have recently participated in other clinical trials or have been under treatment with memantine or acetylcholinesterase inhibitors (e.g., Donepezil, Rivastigmine, Galantamine) must undergo a washout period of at least 4 weeks prior to the start of the study.
6. Capacity to give informed consent based on the clinical judgement of an experienced clinician.
7. The participant has an individual who is in regular, daily contact via phone or in-person visits and who can act as a reliable study partner and provide meaningful input into rating scales.
8. Age \geq 50 years.
9. Fluency in Norwegian and evidence of adequate premorbid intellectual functioning.
10. Capable of participating in all scheduled evaluations and complete all required tests.
11. Females of childbearing potential and males must commit to use highly effective methods of birth control (see highly effective birth control for male and females described in 11.4 appendix 4) from signing informed consent form until at least 30 days after last administration of phenserine or donepezil.

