6.8.4. Anti-Dementia Drugs

If deemed clinically indicated by the study clinician and the participant, participants currently taking anti-dementia drugs (e.g., donepezil, rivastigmine, galantamine, memantine) can participate in the study after a washout period of at least 4 weeks prior to the start of the study intervention. This is to ensure that there are no residual effects of these medications that could interfere with the study results. The washout period ensures that any pharmacodynamic or pharmacokinetic effects from previous medications are minimized, allowing for a clearer assessment of phenserine and donepezil.

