9.1. Screening Visit

During the screening visit, participants will undergo a series of assessments to determine their eligibility for the study.

- During this visit, and before any study procedures are performed, informed consent will be obtained from the participant and caregiver to ensure they understand the study's objectives and willingly agree to participate.
 - This includes a medical evaluation with a detailed medical history review including: concomitant medications, physical examination, Vital signs
 - Safety laboratory tests
 - Urinalysis
 - Physical Exam
 - Neurological Exam, including mental status
 - ECG
 - MRI (if not performed within 2 years)
 - Modified C-SSRS
 - Lumbar puncture (Optional, if not performed previously) for CSF analysis of Alzheimer pathology and storage for subsequent biomarker assessment
 - Venepuncture for blood analysis
- Participants will also be evaluated for their cognitive status using MMSE and CDR
- Review of inclusion/exclusion criteria including confirmation of pathology with validated biomarkers
- If participants are taking any anti-dementia medications, they will be instructed on the washout period required before baseline assessments. If considered relevant, re-screen can be performed.

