9.1 CSF and Plasma Biomarkers

- Change from baseline at Week 8
- Descriptive summaries only
- Correlation analyses with exosome biomarkers (Spearman)

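### Plasma p-tau217/NfL and the CSF markers have no Day 0 sample and the SAP does not define their baseline, so change to Week 8 can start from an early, pre-washout or historical value

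*Protocol*

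**What the plan says.** **Sampling times.** Protocol 9.21 states: "Blood and CSF biomarker samples will be collected at Screening and Week 8". The exosome markers, by contrast, are taken at Baseline and then at each two-weekly visit. Table 1 agrees: the Day 0 column has exosome and AChE samples but no blood or CSF biomarker sample. Protocol 6.3 dispenses drug after all baseline assessments, so the exosome baseline is pre-dose.

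**Analysis.** SAP 9.1 lists "Change from baseline at Week 8" for the CSF and plasma markers, with descriptive summaries and Spearman correlations with the exosome markers. The outcome table in SAP 4.5 gives the timeframe as baseline to Week 8. The SAP does not say which sample is the baseline. It refers to Protocol Section 3 and Table 2 for endpoint definitions, and these do not say either.

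**Washout.** Inclusion criterion 5 (Protocol 5.1) says that participants who have been on these drugs "must undergo a washout period of at least 4 weeks prior to the start of the study". Protocol 6.8.4 says that those currently taking them "can participate in the study after a washout period of at least 4 weeks prior to the start of the study intervention". Protocol 9.1 places the instruction at the screening visit, where "they will be instructed on the washout period required before baseline assessments". A re-screen is optional, and neither 9.1 nor 5.4 says whether biomarker samples are then redrawn.

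**Existing CSF.** Footnote 6 of Table 1 says: "If CSF biomarker data are available then there is no need for a new CSF collection at screening". Protocol 9.1 makes the screening lumbar puncture optional and needed only if none was done before.

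**The concern.** A change score needs a starting value that describes the participant just before treatment. The exosome markers have one. The plasma and CSF markers have only a screening value, which can differ from the Day 0 state in three ways: time has passed, a previous anti-dementia drug may still have been on board, and a CSF result may be old or come from another assay run. Protocol 6.8.4 gives the removal of residual drug effects as the purpose of the washout. An on-drug starting value works against that purpose.

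The stakes are modest but real. Protocol Table 2 presents these markers as the assessment of disease modification, and the study is meant to guide the choice of doses and outcome measures for Phase 2. SAP 9.1 also correlates their changes with exosome changes. In a washout participant, one change could run from an on-drug value and the other from a washed-out value.

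**Working it through.** The plan gives no figure on this point to reproduce. The check uses the visit windows, the washout rule and the allocation.

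**1. Interval.** Inputs: screening Day -28 to 0 (Protocol Table 1); Week 8 at Day 56 ± 3 (SAP 2.4).
- Shortest: 0 + 56 - 3 = 53 days.
- Longest: 28 + 56 + 3 = 87 days.
- On nominal days the longest is 28 + 56 = 84, of which 28 (one third) precede the first dose.
- For an existing CSF result, footnote 6 sets no upper limit.

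**2. When the screening value can be on-drug.** The washout is at least 28 days and the screening window is at most 28 days. A washout begun at the screening visit on Day s fits only if -s ≥ 28, which means exactly Day -28. In that case the screening sample is pre-washout. Any later screening date calls for a re-screen, and the value is then on-drug only if the earlier sample is kept.

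**3. Effect on the analysis.** Let P and D be the effects of phenserine and donepezil on a marker at Week 8, and B the effect of the previous drug still present at screening, taken as the same for everyone concerned. Let p and d be the shares of the phenserine and donepezil arms with an on-drug starting value.
- Within-arm mean change: P - pB and D - dB, instead of P and D.
- Between-arm difference: (P - pB) - (D - dB) = P - D + (d - p)B.

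If p = d the contrast is untouched. Under randomisation p and d have equal expectation, so the expected error is zero. Example with 2 such participants among 16, split 12:4:

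| In donepezil arm | Probability | d - p |
|---|---|---|
| 0 | 66/120 = 0.55 | 0 - 2/12 = -1/6 |
| 1 | 48/120 = 0.40 | 1/4 - 1/12 = 1/6 |
| 2 | 6/120 = 0.05 | 2/4 - 0 = 1/2 |

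Mean: 0.55 × (-1/6) + 0.40 × (1/6) + 0.05 × (1/2) = 0.

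**4. Chance imbalance at 12:4.** The number m with an on-drug value is not in the documents, so it is varied. The probability that none falls in the donepezil arm is C(12,m)/C(16,m):

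| m (assumed) | P(none among the 4) | p when none |
|---|---|---|
| 2 | 66/120 = 55% | 2/12 = 17% |
| 4 | 495/1820 = 27% | 4/12 = 33% |
| 6 | 924/8008 = 12% | 6/12 = 50% |
| 8 | 495/12870 = 4% | 8/12 = 67% |

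With m = 4 and none on donepezil, the contrast is off by B/3. The documents do not give B for any of these markers.

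**The case against.** The strongest reply is that the plan already keeps most on-drug values out. Current treatment with these drugs is exclusion criterion 2, the washout rarely fits inside the screening window, and Protocol 5.4 gives prohibited drug treatment as its example of a reason to re-screen. A re-screen after washout would naturally yield an off-drug sample. This stands in part: the on-drug route is narrow. But no text requires the biomarker sample to be repeated or says which value counts.

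For CSF, footnote 6 can be read as sparing a second lumbar puncture for eligibility, not as naming the baseline for change. The complete-case rule in SAP section 6 might then drop participants without a study-drawn pair. That is a fair reading, but the SAP does not state it. The restriction to in-window assessments in SAP 2.4 names only primary and secondary analyses. Protocol section 9 does confine routine pre-consent procedures to the Table 1 timeframe, while footnote 6 exempts CSF without a time limit. The two need reconciling.

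Three stronger readings are tempting and not supported:
- **That the comparison with donepezil is biased**, because a prior donepezil user gives roughly zero change on donepezil and a switch on phenserine. The same B is subtracted in either arm and cancels in expectation.
- **That one on-drug value among four dilutes the donepezil effect by 25%, and two by 50%.** This needs B = D and ignores the matching shift in the phenserine arm.
- **That the assays differ.** Differing assays are permitted, since entry cut-offs are laboratory-specific and no joint assay is required, but no text says that they occur.

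**Conclusion.** The gap holds: no Day 0 sample, no definition of baseline, and no rule for pre-washout or historical values. For plasma, the certain part is a starting value up to 28 days before Day 0. The on-drug part applies only to participants taking these drugs at screening, and only at Day -28 or where a re-screen does not repeat the sample. For CSF, neither the age of the starting value nor the assay is limited.

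The harm is to within-arm change, to the correlations with exosome changes and, through chance imbalance at 12:4, to the between-arm description. Its size cannot be stated, because neither the share of prior users nor any washout effect on these markers is given. The endpoints are exploratory and descriptive, and the primary exosome endpoint has its own Day 0 baseline. This is a correction worth making because it is cheap. It is not a threat to the trial's main result.

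**What to change.** - **Plasma:** add one aliquot for p-tau217 and NfL at the pre-dose Baseline venepuncture (Protocol 9.3), and define it as baseline in SAP 9.1. Assay each participant's Baseline and Week 8 samples together.
- **Screening plasma and historical CSF:** use for eligibility only.
- **CSF change:** limit to participants with a study-drawn, post-washout CSF and a Week 8 CSF, assayed together. Protocol 9.1 already provides for storage of screening CSF.
- **Wording:** amend Table 1, Protocol 9.21 and SAP 4.5 and 9.1. State whether a re-screen repeats the biomarker samples, and reconcile footnote 6 with the timeframe rule in Protocol section 9.
- **If Day 0 plasma cannot be obtained:** name the screening value as baseline, flag pre-washout values, and show results with and without them.

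The cost is a few extra assays, the amended wording, and fewer CSF pairs in a sample where Week 8 CSF is already voluntary.

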9.22. Health Economics OR Medical Resource Utilization and Health Economics

Health economics and Medical resource utilization are not evaluated in this study.

10. Statistical Considerations

The Statistical Analysis Plan will be completed before the first participant is randomized.

10.1. Randomization Weighting

The purpose of this study is to determine an appropriate dose range of phenserine for a subsequent Phase 2 study aimed at further characterizing phenserine's therapeutic potential for the treatment of people with early or mild AD. The randomization process is weighted 6:2 for phenserine versus donepezil, to ensure that there is adequate data to assess dose response relationships for phenserine, and to be able to compare with direct data from the donepezil arm and for comparison with donepezil's well-established clinical profile.

Early drop outs

Participants who drop out early from the study (before study drug is taken or before first assessment) will be replaced with other eligible recruitment subjects in order to maintain the target sample size and ensure the statistical power of the study is preserved

10.2. Statistical Hypotheses

- **Primary Hypothesis:**

- There is a difference between phenserine and donepezil in terms of their effect on the primary endpoint, which involves changes in exosome biomarkers of pre-programmed cell death, synaptic integrity and function, neuroinflammation, and AD-related protein trafficking.

- **Secondary Hypothesis**

- Phenserine and donepezil do not differ in their safety and tolerability profiles, as measured by the rate and severity of adverse events (AEs).

- **Exploratory Hypothesis:**

- Phenserine has a different effect compared to donepezil on short-term cognitive performance, as measured by the FLAME Memory Composite and other cognitive sub-tests.
- Phenserine and donepezil differ in their effects on changes in blood and cerebrospinal fluid (CSF) biomarkers, including A β 1-40, A β 1-42, Tau, p-tau, p-tau217, and NfL

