10.3.1. General Considerations

The statistical analysis plan for this study is designed to assess the efficacy, safety, and pharmacokinetic properties of phenserine compared to donepezil in participants with early or mild Alzheimer's Disease (AD). Analyses will be conducted on a modified intent-to-treat (mITT) population, which includes all randomized participants who receive at least one dose of study medication and have at least one post-baseline assessment. All statistical tests will be two-sided, with a significance level set at 0.05.

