10.3.5. Secondary Endpoints Analysis

The secondary endpoints include safety and tolerability, cognitive performance, and pharmacokinetic parameters. Safety and tolerability will be assessed by comparing the incidence and severity of adverse events (AEs) between treatment groups.

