10.3.7. Safety Analyses

Safety analysis will involve descriptive analysis comparing frequencies between the two treatment groups with frequency AEs and SAEs.

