2.3.1 Hypothesis Framework

This trial is an exploratory Phase 1b dose range–finding study designed to characterize the pharmacodynamic, pharmacokinetic, and safety profile of phenserine compared with donepezil in participants with early or mild Alzheimer's disease. The study is not powered for formal confirmatory hypothesis testing.

The primary objective is mechanistic and descriptive in nature, focusing on changes in exosome-derived biomarkers associated with pre-programmed cell death, synaptic integrity, neuroinflammation, and AD-related protein trafficking.

Primary Hypothesis Framework

- Null hypothesis (H_0): There is no difference between phenserine and donepezil in changes from baseline in exosome biomarkers over the 8-week treatment period.
- Alternative hypothesis (H_1): Treatment with phenserine is associated with changes from baseline in exosome biomarkers that differ from those observed with donepezil over the 8-week treatment period.

These hypotheses will be **exploratorily** evaluated through estimation of treatment effects and their associated uncertainty (95% confidence intervals), rather than formal hypothesis testing with a pre-specified significance level. The focus is on estimating the magnitude and direction of treatment differences.

Secondary and Exploratory Analyses

There is a single identified primary analysis related to exosome biomarker changes. All secondary (safety, PK, AChE inhibition, compliance) and exploratory (CSF, plasma biomarkers, cognitive outcomes) analyses will be considered supportive or exploratory and will be interpreted descriptively.

No formal non-inferiority or superiority margins are prespecified, and no multiplicity adjustments will be applied.

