2.3.2 Confidence Intervals and p-values

P-values will be reported for descriptive purposes only and will be interpreted cautiously in the context of the exploratory study design. All efficacy estimates will be presented with two-sided 95% confidence intervals, which should be interpreted as ranges of plausible treatment effects rather than formal inference tools. As there is only one primary null hypothesis to be tested in this trial, there will be no adjustments for multiplicity.

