2.4 Timing of Outcome Assessments

The timing of all outcome assessments is predefined in the study protocol and summarized in the Schedule of Activities (SoA) (Protocol Section 1.3, Table 1). Outcome measures are collected at screening, baseline, and at scheduled on-treatment and follow-up visits during the 8-week treatment period and safety follow-up.

For all clinically planned outcome measures, visits should occur within the predefined visit windows. Assessments performed outside the allowable visit window will be considered protocol deviations, unless otherwise justified and documented. Only assessments obtained within the protocol-specified windows will be used for primary and secondary analyses.

The target days and visit windows relevant for efficacy, pharmacodynamic, pharmacokinetic, and safety analyses are defined as follows:

Visit Label	Visit Window
Screening	Within 28 days prior to baseline
V1: Baseline / Randomization	Day 0
V2: Week 2	Day 14 ± 3 days
V3: Week 4	Day 28 ± 3 days
V4: Week 6	Day 42 ± 3 days
V5: Week 8 / End of Treatment	Day 56 ± 3 days
Safety Follow-up / EOS	Within 28 days after last dose

Assessments collected outside the visit window will not be included in the primary analysis but may be listed and summarized descriptively.

3 Study Design Overview

- Design: Open-label, randomized (6:2), parallel-group Phase 1b study
- Treatment Arms:
 - Phenserine (dose-escalation up to 10 mg TDS)
 - Donepezil (5–10 mg OD)
- Treatment Duration: 8 weeks
- Sample Size: n = 16 (Phen: n=12; Donepezil: n=4)

Given the exploratory nature and small sample size, all analyses will be descriptive, and estimation focused.

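### The protocol's secondary hypothesis of no safety difference between the arms has no margin, cannot be supported by 12 versus 4 participants, and is left standing beside a descriptive safety plan

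*Protocol*

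**What the plan says.** Safety and tolerability are the key secondary objective (Protocol 3). The matching hypothesis in Protocol 10.2 reads: "Phenserine and donepezil do not differ in their safety and tolerability profiles, as measured by the rate and severity of adverse events (AEs". The primary and exploratory hypotheses in the same list all assert a difference; only the safety hypothesis asserts that there is none.

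Protocol 10.3.1 gives a general rule: "All statistical tests will be two-sided, with a significance level set at 0.05". Protocol 10.3.5 adds: "Safety and tolerability will be assessed by comparing the incidence and severity of adverse events (AEs) between treatment groups". Neither section names a safety test. Protocol 10.3.7 describes the analysis itself: "Safety analysis will involve descriptive analysis comparing frequencies between the two treatment groups with frequency AEs and SAEs".

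The SAP takes the descriptive line. Section 2.3.1 sets null and alternative hypotheses for the primary endpoint only, places safety among the analyses to be interpreted descriptively, and says: "No formal non-inferiority or superiority margins are prespecified". Section 2.3.2 makes p-values descriptive. Section 3 calls all analyses descriptive and estimation-focused and gives the size: "Sample Size: n = 16 (Phen: n=12; Donepezil: n=4". Section 5 rules out formal hypothesis testing.

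On intervals, SAP 2.3.2 states: "All efficacy estimates will be presented with two-sided 95% confidence intervals". SAP 5 puts general emphasis on confidence intervals but summarises categorical variables by counts and percentages. SAP 8.1 lists adverse-event and SAE incidence, gastrointestinal events, dose reductions and discontinuations by arm, with no interval for any of them.

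**The concern.** A claim that two treatments have the same safety needs a margin and an interval narrow enough to lie inside it. Without a margin, the only apparent support for such a claim is failing to see a difference, and a very small trial often fails to see one whatever the truth. The SAP's descriptive approach does not remove the problem, because it never says that the Protocol 10.2 hypothesis is dropped, and its safety section shows frequencies without their uncertainty.

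The results are meant to inform dose selection and design for a longer Phase 2 study, and Protocol 10.3 justifies the extra phenserine participants partly by their value for safety reporting. A report that sets similar-looking percentages from 12 and 4 people beside a no-difference hypothesis could be taken as evidence of comparable safety when the data are compatible with a large excess of events.

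**Working it through.** **Inputs from the documents.** 12 phenserine and 4 donepezil participants (SAP 3); no margin (SAP 2.3.1); two-sided 0.05 as a general rule (Protocol 10.3.1). The documents give no adverse-event rate for donepezil, so the rates in step 2 are assumptions. Fisher's exact test and the uncorrected chi-square test are used for illustration; the documents name neither.

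**Step 1: the plan's own figure.** No power or precision is stated for safety. The only power statement is for the biomarkers: 4 per arm for 80% power at 2.45 SD. It reproduces: the noncentral t gives 61.9% with 3 per arm and 82.1% with 4. It says nothing about adverse-event rates.

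**Step 2: what a comparison could detect.** Power is the sum, over the 13 x 5 possible tables with p <= 0.05, of Bin(x; 12, p_phen) x Bin(y; 4, p_don). For 50% versus 20%:

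- Fisher rejects in the harmful direction at 9/12 or more against 0/4, 11/12 or more against 1/4, and 12/12 against 2/4. The first two give 0.4096 x 0.0730 + 0.4096 x 0.0032 = 0.0299 + 0.0013. All other tables add about 0.0003. Power is 3.1%, so the result is non-significant 96.9% of the time.
- Chi-square rejects at 7/12 or more against 0/4 and 10/12 or more against 1/4: 0.4096 x 0.3872 + 0.4096 x 0.0193 = 0.1586 + 0.0079. All other tables add about 0.0012. Power is 16.8%, so the result is non-significant 83.2% of the time.

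Further Fisher results, phenserine versus donepezil:

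| Assumed true rates | Non-significant |
|---|---|
| 30% vs 10% | 99.8% |
| 60% vs 20% | 89.9% |
| 80% vs 20% | 55.1% |
| 80% vs 10% | 39.5% |

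The choice of test matters. An observed 8/12 versus 0/4 gives p = 0.077 by Fisher and 0.021 by chi-square.

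**Step 3: what equal observed rates would show.** Take 3/12 and 1/4, both 25%. The Wilson 95% limits are 8.9% to 53.2% and 4.6% to 69.9%. Newcombe's limits for the difference (phenserine minus donepezil) are:

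- lower: -sqrt[(0.250 - 0.089)^2 + (0.699 - 0.250)^2] = -0.477
- upper: +sqrt[(0.532 - 0.250)^2 + (0.250 - 0.046)^2] = +0.349

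Identical percentages are therefore compatible with anything from 48 points fewer to 35 points more events on phenserine.

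**Step 4: what zero events would show.** The one-sided 95% upper bound is 1 - 0.05^(1/n): 22.1% for 0/12 and 52.7% for 0/4.

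**Step 5: could a margin rescue the hypothesis?** For non-inferiority with equal true rates p, 3:1 allocation, one-sided 0.025 and 80% power, the donepezil arm needs (1.960 + 0.842)^2 x p(1-p) x (1 + 1/3) / margin^2. With a 30-point margin and p = 10%, this is 10.5, so 11 on donepezil and 44 in total. With a 20-point margin and p = 20%, it is 41.9, so 42 and 168 in total. These margins and rates are assumptions, but even the generous first case needs well over 16.

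**The case against.** The strongest reply is that no safety hypothesis is tested. A reader might infer from Protocol 10.2 and the 0.05 rule in 10.3.1 that safety will be tested at 0.05 and a non-significant result counted as support. The documents do not say so. Protocol 10.3.1 is a general rule, 10.3.7 makes the safety analysis descriptive, and SAP 2.3.1, 2.3.2, 3 and 5 rule out formal testing and make p-values descriptive. Neither document says that a non-significant or similar-looking result will be read as similar safety. Participant protection also does not depend on a between-arm p-value: it rests on the dose-limiting rule in Protocol 2.3.1, the stopping criteria in 7.1 and DSMB review.

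A reader might also infer that a harmful difference would almost always be missed. That depends on its size and on the test. It is a fair description of differences up to about 30 points under Fisher, but not of very large ones, as the 80% versus 10% result shows.

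Finally, SAP 5 does emphasise confidence intervals in general, so it would be wrong to say that the SAP confines them to efficacy.

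All of this stands, and it limits the point to wording and reporting. It does not remove the point: the 10.2 sentence remains, the SAP does not withdraw it, and SAP 8.1 specifies no interval for adverse-event incidence.

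**Conclusion.** The concern holds as an unsupportable hypothesis that conflicts with the descriptive safety plan, together with a gap in the planned safety reporting. It does not hold as a planned 0.05 safety test or as a rule that non-significance shows equal safety. No planned analysis is invalid.

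The clearest measure of size needs no assumed true rates: equal observed rates of 3/12 and 1/4 leave a 95% interval of about -48 to +35 points. The 83% to 97% chance of a non-significant result applies to assumed true rates of 50% versus 20% and to the two tests shown; larger differences would be missed less often. The change is worth making because safety is the key secondary endpoint and the remedy is nearly free.

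**What to change.** 1. In Protocol 10.2, replace the no-difference sentence with an estimation aim: to estimate adverse-event incidence and severity in each arm, and the difference between arms, with 95% confidence intervals. Adding a margin instead is not feasible with 16 participants.
2. In SAP 8.1, report exact 95% intervals in each arm for the incidence of adverse events, SAEs, gastrointestinal events and discontinuations due to adverse events, and a 95% interval for the phenserine-minus-donepezil risk difference, naming the method (Newcombe, for example).
3. Where no event is seen, report the upper bound and say which one is used. The one-sided 95% bound is 22% for 0/12 and 53% for 0/4; the upper limit of the two-sided exact interval is 26% and 60%.
4. In SAP 2.3.1, state that a non-significant or similar-looking safety result will not be read as evidence of similar safety, and that this replaces the secondary hypothesis in Protocol 10.2.

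The cost is protocol and SAP wording and a few table columns. No visit, sample or participant changes. The downside is that the intervals will look wide, which is an accurate account of what 12 and 4 participants can show.
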